4.1. Protocol Deviations

Significant protocol deviations (including deviations related to study inclusion/exclusion criteria, conduct of the trial, patient management or patient assessment) will be summarised and listed.

Protocol deviations will be tracked by the study team throughout the conduct of the study in accordance with the Protocol Deviation Management Plan.

- Data will be reviewed prior to freezing the database to ensure all significant deviations and deviations which may lead to exclusion from the analysis are captured and categorised on the protocol deviations dataset.

- This dataset will be the basis for the summaries and listings of protocol deviations.

A separate listing of all inclusion/exclusion criteria deviations will also be provided. This listing will be based on data as recorded on the inclusion/exclusion page of the electronic case report form (eCRF).

5. CONSIDERATIONS FOR DATA ANALYSES AND DATA HANDLING CONVENTIONS

5.1. Study Treatment & Sub-group Display Descriptors

Only one treatment, oral gepotidacin 1500 mg BID will be administered in this study as the study treatment.

5.2. Baseline Definitions

For all endpoints (except as noted in baseline definitions) the baseline value will be the latest predose assessment with a non-missing value, including those from unscheduled visits. If time is not collected, Day 1 assessments are assumed to be taken prior to first dose and used as baseline.

Parameter	Study Assessments Considered as Baseline		Baseline Used in Data Display
	Day -1	Day 1 (Predose)	
Efficacy			
Acute Cystitis Signs and Symptoms	X		Day -1
Gram Stain		X	Day 1 (Predose)
Quantitative Bacteriology Culture		X	Day 1 (Predose)
In Vitro Antimicrobial Susceptibility Test		X	Day 1 (Predose)
Safety			
12-lead Electrocardiogram (ECG)	X	X	Day 1 (Predose) ^[1]
Vital Sign	X	X	Day 1 (Predose) ^[1]
Hematology	X		Day -1
Clinical Chemistry	X		Day -1
Urinalysis	X		Day -1

- Vital sign and ECG assessments at predose on Day 1 will be only performed if the Day -1 assessment is not within 4 hours of the first dose of study treatment. If the Day 1 predose assessments are not performed, Day -1 assessments will be used as baseline in data display. Average of the triplicate ECG assessment at Day -1 will be used as the baseline if Day 1 predose assessment is not performed as described in [Appendix 4: Derived and Transformed Data](#).

Unless otherwise stated, if baseline data is missing no derivation will be performed and baseline will be set to missing.

5.3. Other Considerations for Data Analyses and Data Handling Conventions

Other considerations for data analyses and data handling conventions are outlined in the appendices:

Section	Component
12.1	Appendix 1 : Schedule of Activities
12.2	Appendix 2 : Study Phases and Treatment Emergent Adverse Events
12.3	Appendix 3 : Data Display Standards & Handling Conventions
12.4	Appendix 4 : Derived and Transformed Data
12.5	Appendix 5 : Reporting Standards for Missing Data
12.6	Appendix 6 : Values of Potential Clinical Importance
12.7	Appendix 7 : Division of Microbiology and Infectious Disease Adult Toxicity Tables for Adverse Event Assessment
12.8	Appendix 8 : Abbreviations & Trade Marks
12.9	Appendix 9 : List of Data Displays

6. STUDY POPULATION ANALYSES

6.1. Overview of Planned Study Population Analyses

The study population analyses will be based on the “ITT” population, unless otherwise specified.

Study population analyses including analyses of subject’s disposition, protocol deviations, demographic and baseline characteristics, prior and concomitant medications, and exposure and treatment compliance will be based on GSK Core Data Standards. Baseline disease characteristics including baseline uropathogen recovery rate (including drug-resistant uropathogens), baseline clinical symptom score, current medication conditions, and exposure data will be summarized. History of uncomplicated urinary tract infection will be listed.

The details of data displays are presented in [Appendix 9: List of Data Displays](#).

7. PHARMACOKINETIC ANALYSES

7.1. Primary Pharmacokinetic Analyses

7.1.1. Endpoint / Variables

7.1.1.1. Drug Concentration Measures

Refer to [Appendix 3: Data Display Standards & Handling Conventions \(Section 12.3.3 Reporting Standards for Pharmacokinetic\)](#). Only total gepotidacin plasma PK concentrations will be measured and reported in the bioanalytical data. Therefore, unbound plasma PK concentrations will be derived by multiplying the total plasma PK concentrations by 0.67, to correct for the low plasma protein binding of gepotidacin (33%) observed in previous studies.

7.1.1.2. Derived Pharmacokinetic Parameters

Pharmacokinetic parameters will be calculated by standard non-compartmental analysis according to current working practices and using the currently supported version of Phoenix WinNonlin version 6.4 or higher. All calculations of non-compartmental parameters will be based on actual sampling times. Pharmacokinetic parameters listed will be determined from the plasma and urine concentration-time data, as data permits. [Table 2](#) provides the details of derived plasma PK parameters.

Table 2 Derived Plasma Pharmacokinetic Parameters

Parameter	Parameter Description
AUC(0- τ)	Area under the concentration-time curve (AUC) from time 0 to the 12-hour dosing interval, to be calculated using the linear trapezoidal rule for each incremental trapezoid and the log trapezoidal rule for each decremental trapezoid. Calculated from Days 1 and 4.
AUC(0-24)	Area under the concentration-time curve (AUC) from time 0 to the 24-hour, calculated as: $AUC(0-24) = AUC(0-\tau) \times 2$ Calculated for Day 4.
C _{max}	Maximum observed concentration, determined directly from the concentration-time data. Calculated from Days 1 and 4.
T _{max}	Time to first occurrence of C _{max} . Calculated from Days 1 and 4.
CL _{ss} /F	Apparent steady state clearance (Day 4 only), calculated as $CL_{ss}/F = \text{Dose}/AUC(0-\tau)$
R _o	Accumulation ratio (Day 4 only), calculated as: $R_o = AUC(0-\tau) \text{ Day 4}/AUC(0-\tau) \text{ Day 1}$
C _{τ}	Observed predose (nominal time = 0) concentrations on Days 1 through 5

NOTES:

- Additional parameters may be included as required.

7.1.2. Summary Measure

Summary statistics (arithmetic mean, geometric mean, median, standard deviation (SD), minimum, maximum, and coefficient of variation [CV]) for plasma gepotidacin PK parameter values will be summarized by study day, as appropriate. The C_{τ} will be summarized and used to assess achievement of steady state. Gepotidacin plasma PK parameter estimates will be listed by participant and study day.

7.1.3. Population of Interest

The primary pharmacokinetic analyses will be based on the Pharmacokinetic population and Pharmacokinetic Parameter population, unless otherwise specified.

7.1.4. Statistical Analysis / Methods

Details of the planned displays are provided in [Appendix 9: List of Data Displays](#) and will be based on GSK Data Standards and statistical principles.

Unless otherwise specified, endpoints / variables defined in Section [7.1.1](#) will be summarised using descriptive statistics, graphically presented (where appropriate) and listed.

7.1.4.1. Statistical analysis of Pharmacokinetic Parameters

All the derived parameters described in [Table 2](#) will be listed. For each of these parameters, except T_{max} , the following summary statistics will be calculated for each active treatment group: median, maximum, minimum, arithmetic mean, SD, CV on arithmetic mean, geometric mean, CV on geometric mean, 95% confidence interval (CI) for the geometric mean, and SD of logarithmically transformed data. For t_{max} , t_{min} , and t_{lag} , median, maximum, minimum, arithmetic mean, and SD will be calculated.

The following pharmacokinetic statistical analyses will only be performed if sufficient data is available (i.e. if participants have well defined plasma profiles).

Endpoint / Variables

 Plasma primary PK endpoints include predose concentrations (C_{τ}) Day 1 through Day 5
Model Specification

 To assess the achievement of steady state, C_{τ} concentrations between Days 1 through 5 for each treatment. A linear mixed model using Day as fixed effects and subject as a random effect on the ln-transformed pre-dose values will be performed evaluating whether steady state was achieved using Helmert transformation approach. The comparison will begin with Day 1 vs the average of Days 2, 3, 4 and 5. The ratio of geometric least square means and its 95% CI will be presented for the comparison(s).
Model Results Presentation

 Statistical analysis of steady state will be analyzed using Helmert transformation approach.

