- Serial blood PK sampling will be performed for the first dose of study treatment on Day 1 and for the time-matched dose on Day 4. Blood samples will be collected predose and at 0.5, 1, 1.5, 2, 3, 4, 6, 8, and 12 hours postdose.
- Serial urine PK sampling will be performed for the first dose of study treatment on Day 1 and for the time-matched dose on Day 4. Urine samples will be collected predose and at intervals of 0 to 2 hours, 2 to 4 hours, 4 to 6 hours, 6 to 8 hours, 8 to 10 hours, and 10 to 12 hours postdose.
- Predose PK blood samples will be collected before each time-matched dose on Days 1 through 5. Predose PK urine samples will be collected 0 to 2 hours before each time-matched dose on Days 1 through 5. Only 1 sample is needed when serial and predose samples overlap.
- Participants will check-out of the clinic after all study procedures have been performed, including a predose clean-catch midstream urine sample for Gram stain, quantitative bacteriology culture, and antimicrobial susceptibility testing, predose PK sample collections, and safety assessments. Participants should remain in the clinic to complete a total of 10 doses. Participants will be instructed to return for the TOC (Day 10 to 13) and Follow-up (Day 28±3) Visits.

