20. The participant has a recent history of vasovagal syncope or episodes of symptomatic bradycardia or bradyarrhythmia within the last 12 months.
21. The participant is taking QT-prolonging drugs or drugs known to increase the risk of torsades de points (TdP) per the www.crediblemeds.org "Known Risk of TdP"

category at the time of her Baseline Visit, which cannot be safely discontinued from the Baseline Visit to the TOC Visit; or the participant is taking a strong cytochrome P450 enzyme 3A4 (CYP3A4) inhibitor or a strong P-glycoprotein (P-gp) inhibitor.

Cardiac ECG Exclusion

22. The participant has a QTc >450 msec or a QTc >480 msec for participants with bundle-branch block. **Note:** The QTc is the QT interval corrected for heart rate according to either Bazett or Fridericia formula, machine, or manual overread.

Hepatic Exclusions

23. The participant has a known alanine transferase (ALT) value >2 × upper limit of normal (ULN).
24. The participant has a known bilirubin value >1.5 × ULN (isolated bilirubin >1.5 × ULN is acceptable if bilirubin is fractionated and direct bilirubin <35%).
25. The participant has a current or chronic history of liver disease, or known hepatic or biliary abnormalities (with the exception of Gilbert's syndrome or asymptomatic gallstones), including symptomatic viral hepatitis or moderate-to-severe liver insufficiency (Child Pugh class B or C). **Note:** Participants with asymptomatic viral hepatitis are eligible for study participation.

Prior Antibiotic/Antifungal Use Exclusion

26. The participant has received treatment with other systemic antimicrobials or systemic antifungals within 1 week before study entry.

Concomitant Medication Use Exclusion

27. The participant must agree not to use the medications or nondrug therapies from the Baseline Visit through the TOC Visit as detailed in Section [7.7.2](#).

Prior/Concurrent Clinical Study Experience

28. The participant has been previously enrolled in this study or has previously been treated with gepotidacin.
29. The participant has participated in a clinical trial and has received an investigational product within 30 days or 5 half-lives, whichever is longer.

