12.9.8. Pharmacokinetic Tables

Pharmacokinetic: Tables					
No.	Population	IDSL / Example Shell	Title	Programming Notes	Deliverable
Pharmacokinetic Concentrations					
4.1.	PK Concentration	PKCT1	Summary of Gepotidacin Plasma Pharmacokinetic Concentration-Time Data (units)		SAC
4.2.	PK Concentration	PKCT1	Summary of Gepotidacin Urine Pharmacokinetic Concentration-Time Data (units)		SAC
4.3.	PK Concentration	PKCT1	Summary of Gepotidacin Cervical, Rectal, and Pharyngeal Pharmacokinetic Concentration-Time Data (units)		SAC
Pharmacokinetic Parameters					
4.4.	PK Parameter	PKPT4	Summary Statistics of Derived Gepotidacin Plasma Pharmacokinetic Parameters	Free and total PK Parameters include: AUC(0-tau) (units), AUC(0-24) (units), Cmax (units), Tmax (units), CLss/F (units), Ro (units), Ctau (units). Do not In-transform Tmax. Ctau will have values for Day 1 through 5	SAC
4.5.	PK Parameter	PKPT4	Summary Statistics of Derived Gepotidacin Urine Pharmacokinetic Parameters	Parameters include: Ae12h (units), A(t1-t2) (units), %fe (units), CLr (units), Ctau (units), AUC(0-tau) (units), and AUC(0-24) (units) for all subjects; Ae(t1-t2) include Ae(0-2) (units), Ae(2-4) (units), Ae(4-6) (units), Ae(6-8) (units), Ae(8-10) and Ae(10-12) (units). Ctau has values on Day 1 through Day 5	SAC
4.6.	PK Parameter	PK_T1	Statistical Analysis of Gepotidacin Plasma Predose	Ctau values of day 1 through 5	SAC

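### The steady-state model opens by contrasting the drug-free Day 1 predose sample on the log scale, so its first comparison says nothing about steady state; it should start at Day 2

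*SAP*

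**What the plan says.** SAP Table 2 (section 7.1.1.2) defines plasma Cτ as "Observed predose (nominal time = 0) concentrations on Days 1 through 5". SAP 7.1.4.1 then specifies the steady-state analysis: "A linear mixed model using Day as fixed effects and subject as a random effect on the ln-transformed pre-dose values will be performed", evaluated by Helmert transformation. On the order of comparisons it says: "The comparison will begin with Day 1 vs the average of Days 2, 3, 4 and 5". Results are to be shown as ratios of geometric least squares means with 95% confidence intervals. The programming note for Table 4.6 (SAP 12.9.8) confirms the input: "Ctau values of day 1 through 5".

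The same section asks for a geometric mean with its 95% CI and CV, and the SD of logged data, for every Table 2 parameter except Tmax. That includes Day 1 Cτ.

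Protocol 5.1 fixes what the Day 1 sample is: "Serial blood PK sampling will be performed for the first dose of study treatment on Day 1 and for the time-matched dose on Day 4". Exclusion criterion 28 (Protocol 6.2) bars anyone who "has previously been treated with gepotidacin".

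**The concern.** A sample drawn before a participant's first exposure cannot show whether repeat dosing has reached a plateau, and a concentration of zero has no logarithm. Yet the SAP makes this sample one side of its lead comparison. A programmer who follows the text literally gets either a contrast that cannot be computed or a number produced by an imputation rule that the SAP does not reproduce.

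Plasma Cτ on Days 1 to 5 is among the primary endpoints (Protocol 4, SAP 2.2), and Table 4.6 is the only model-based analysis among the PK tables. Two Day 4 quantities are interpreted on the assumption of steady state: CLss/F, and AUC(0-24) taken as twice AUC(0-τ). The latter feeds the AUC/MIC ratios in SAP section 10. A clean check on steady state is therefore worth having.

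**Working it through.** **Plan's own figure.** The documents give none for the steady-state analysis. The only precision statement (Protocol 10.1) concerns AUC and Cmax with about 20 completers. It reproduces as t(0.975, 19) × CV/√20: 10.2% and 13.9% for AUC (CVs 21.9% and 29.6%), and 18.9% and 14.6% for Cmax (CVs 40.3% and 31.1%). These lie within the stated 15% and 20%. Nothing below depends on them.

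**Step 1: is the Day 1 value drug-free?** Predose blood is drawn before each time-matched dose (Protocol Table 1, footnote k), and the first dose sets that time (Protocol 9, On-Therapy Visit). Protocol 9 lists predose PK blood among the Day 1 predose assessments. Prior gepotidacin is excluded. No sentence states that the value is zero. That is an inference, but only a protocol deviation or assay contamination would make it false.

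**Step 2: the first contrast under each way of handling the value.**

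- Kept as zero: ln(0) is undefined.
- Set to missing: there is no Day 1 mean, so the contrast cannot be estimated.
- Imputed as a constant c: the ratio equals c/G, where G is the geometric mean over Days 2 to 5.

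Illustration (assumed: n = 20, sb = 0.5, sw = 0.25, troughs of 0.30 to 0.40 µg/mL; one simulated data set). The ratio was 0.0279 at c = 0.01 µg/mL (95% CI 0.0250 to 0.0313), so G = 0.01/0.0279 ≈ 0.358. At c = 0.005, 0.001 and 0.00001 it was 0.0140, 0.0028 and 0.000028. Every interval lies far below 1.

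**Step 3: later contrasts if Day 1 is imputed and kept.** Let log trough on Days 2 to 5 be a day mean plus a subject effect (variance sb²) plus error (variance sw²), with Day 1 constant. The covariance matrix S of one participant's five values has zeros for Day 1 and sb² + sw² on the diagonal (sb² off it) for the other four days. The expected residual mean square is [trace(S) − 1′S1/5]/4:

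- trace(S) = 4sb² + 4sw²
- 1′S1/5 = (16sb² + 4sw²)/5 = 3.2sb² + 0.8sw²
- difference divided by 4 = 0.2sb² + 0.8sw²

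Without Day 1 it is sw². The factor is therefore 0.8 + 0.2(sb/sw)². CI width on the log scale changes by the square root of this, times t(0.975, 76)/t(0.975, 57). The documents give neither SD, so the table shows a range of assumptions (n = 20, 4,000 simulated data sets per row).

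| sb | sw | Factor (formula) | Residual MS with / without Day 1 | Simulated ratio | CI width ratio |
|---|---|---|---|---|---|
| 0.2 | 0.3 | 0.889 | 0.0802 / 0.0902 | 0.889 | 0.94 |
| 0.3 | 0.3 | 1.0 | 0.0898 / 0.0899 | 0.999 | 0.99 |
| 0.4 | 0.2 | 1.6 | 0.0640 / 0.0398 | 1.607 | 1.26 |
| 0.5 | 0.25 | 1.6 | 0.0998 / 0.0624 | 1.599 | 1.26 |
| 0.6 | 0.2 | 2.6 | 0.1035 / 0.0399 | 2.593 | 1.60 |

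**Step 4: what moves and what does not.** In one simulated data set with sb = 0.6 and sw = 0.2, Day 2 versus the mean of Days 3 to 5 gave a ratio of 0.831 whether or not Day 1 was in the model. The 95% CI was 0.746 to 0.925 without Day 1 and 0.716 to 0.964 with it. The later estimates and intervals were the same for every c. If Day 1 drops out as missing, nothing changes.

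**The case against.** The strongest reply is that the defect is contained. The text says only that the sequence begins with Day 1. A failed or trivially extreme first step does not prevent the Day 2, Day 3 and Day 4 contrasts, which are the useful ones. Cτ is also tabulated (Table 4.4) and plotted individually and as means and medians (Figures 4.2, 4.6 and 4.9), so the approach to steady state on Days 2 to 5 will be visible anyway. The study tests no hypothesis (Protocol 10, SAP 2.4). All of this stands. It limits the severity but does not give the first contrast a meaning.

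A reader might infer four stronger things that the documents do not support.

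- *All later contrasts are distorted.* This needs Day 1 to be imputed and kept. Even then point estimates hold in balanced data, and the intervals can narrow as well as widen. Where troughs are missing on other days, small shifts in the estimates are possible. The only CVs given (21.9% to 40.3%) are for AUC and Cmax and do not separate sb from sw.
- *Wider intervals favour declaring steady state.* The SAP states no decision rule. A wide interval helps if steady state is read from non-significance and hurts if it is read from equivalence.
- *The analyst picks the imputed value.* SAP 12.3.3 refers imputation to internal guidance (GUI_51487) whose content is not given. The fair statement is that the SAP does not reproduce the rule. Whatever that rule says, one of the three outcomes in Step 2 follows.
- *CLss/F, Ro and AUC(0-24) depend on this model.* They are computed by formula and not conditioned on it. Ro is an observed ratio of two AUCs and needs no declaration of steady state.

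The SAP does make the analysis conditional on sufficient data, but explains this as well-defined plasma profiles. That does not exempt Day 1.

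**Conclusion.** The point holds for the first contrast. As written, Day 1 versus the mean of Days 2 to 5 is undefined, inestimable or a restatement of the imputation rule. This rests on the Day 1 sample being drug-free, which follows from its timing and exclusion criterion 28. It does not rest on any assumed variance or assay limit.

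The effect on later contrasts is conditional. With Day 1 imputed and kept, their intervals use the wrong residual variance: wider when sb exceeds sw, slightly narrower when sb is the smaller. The range of 0.94 to 1.60 reflects the SDs assumed here and is not a prediction for this trial.

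Log-scale summaries of Day 1 Cτ have the same log-of-zero problem. Overall this is a should-fix to one supportive model-based analysis. It does not threaten the descriptive PK results, so it is not a must-fix.

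**What to change.** - In SAP 7.1.4.1, exclude Day 1 from the steady-state model. Define the Helmert sequence as Day 2 versus the mean of Days 3, 4 and 5; then Day 3 versus the mean of Days 4 and 5; then Day 4 versus Day 5.
- Change the Table 4.6 programming note to Days 2 through 5.
- In Table 4.4, omit the geometric mean, its CI and CV, and the SD of logs for Day 1 Cτ. Keep Day 1 values in the listings as a pre-exposure check.
- State in the SAP how values below quantification on any other day enter the model.
- Record the change in SAP Table 1 (section 2.1), because Protocol 10.3.1 lists Day 1 Cτ among the primary parameters and asks for geometric means.

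Every remaining contrast is then defined and free of any Day 1 imputation constant. The cost is a short SAP edit, two table notes and one row in the change table. Sampling and data collection are unchanged.

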7.2. Secondary Pharmacokinetic Analyses

7.2.1. Endpoint / Variables

7.2.1.1. Drug Concentration Measures

Refer to [Appendix 3: Data Display Standards & Handling Conventions \(Section 12.3.3 Reporting Standards for Pharmacokinetic\)](#).

7.2.1.2. Derived Urine Pharmacokinetic Parameters

Pharmacokinetic parameters will be calculated by standard non-compartmental analysis according to current working practices and using the currently supported version of SAS version 9.3. All calculations of non-compartmental parameters will be based on actual sampling times. Pharmacokinetic parameters listed will be determined from the urine concentration-time data, as data permits.

Table 3 Derived Urine Pharmacokinetic Parameters

Parameter	Parameter Description
Ae 12h	Total unchanged drug excreted over 12 hours (total amount of drug excreted in urine), calculated by adding all the fractions of drug collected over all the allotted time intervals. Calculated from Days 1 and 4.
Ae(t1-t2)	Amount of drug excreted in urine in time intervals for predose, 0 to 2 hours, 2 to 4 hours, 4 to 6 hours, 6 to 8 hours, 8 to 10, and 10 to 12 hours postdose. Calculated from Days 1 and 4.
AUC(0-τ)	Area under the urine concentration-time curve (AUC) from time 0 to the 12-hour dosing interval, to be calculated using the linear trapezoidal rule for each incremental trapezoid and the log trapezoidal rule for each decremental trapezoid. Calculated from Days 1 and 4.
AUC(0-24)	Area under the urine concentration-time curve (AUC) from time 0 to the 24-hour, calculated as: $AUC(0-24) = AUC(0-\tau) \times 2$ Calculated Day 4.
fe%	Percentage of the given dose of drug excreted in urine, calculated as: $fe\% = (Ae\ 12h/Dose) \times 100$ Calculated for Days 1 and 4
CLr	Renal clearance of drug, calculated as: $CLr = Ae\ 12h/AUC(0-\tau)$ Calculated from Days 1 and 4.
C _τ	Observed predose (nominal time = 0) urine concentrations on Days 1 through 5.

NOTES:

- Additional parameters may be included as required.

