9.5. Pharmacokinetics

9.5.1. Blood and Urine Samples

- Blood and urine samples for PK analysis of gepotidacin will be collected at the time points indicated in [Table 1](#) and [Table 2](#). The actual date and time of each sample collection will be recorded. The volume of blood required for each PK sample is approximately 3 mL.
- During the On-Therapy Visit, when the predose urine PK collection coincides with the predose urine bacteriology sample collection, a single urine sample of adequate volume may be collected and split into separate samples for PK and microbiological purposes. **Note:** The date and time of the last dose taken before the predose PK collection will be recorded.
- If a participant is switched to a different antibiotic before the end of study treatment, a final blood and urine PK sample should be collected prior to

administration of the different antibiotic. The actual date and time of each sample collection will be recorded.

- Collection, processing, storage, and shipping procedures for blood and urine PK samples are provided in the SRM and/or laboratory manual.
- Plasma PK parameters for gepotidacin will include AUC(0- τ), C_{max}, t_{max}, CL_{ss}/F, R_o, and C _{τ} . Urine PK parameters for gepotidacin will include Ae 12h, Ae(t1-t2), fe%, CL_r, and C _{τ} .

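### SAP Table 3 lists the predose sample as an Ae interval, so Ae 12h coded as written would count more than 12 hours of urine on Day 4 and conflict with its own label

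*SAP*

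**What the plan says.** SAP Section 7.2.1.2, Table 3, gives the derivations of the urine parameters for Days 1 and 4:

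- The Ae(t1-t2) row begins "Amount of drug excreted in urine in time intervals for predose, 0 to 2 hours, 2 to 4 hours, 4 to 6 hours" and continues in 2-hour steps to 12 hours. Predose is the first interval named.
- The Ae 12h row opens with "Total unchanged drug excreted over 12 hours" and says it is "calculated by adding all the fractions of drug collected over all the allotted time intervals". Nothing excludes predose.
- fe% is Ae 12h over dose, times 100. CLr is Ae 12h over AUC(0-τ). The only AUC(0-τ) defined in Table 3 is a urine AUC. Table 2 uses the same symbol for plasma.

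Other parts of the plan point the other way. The programming note for Table 4.5 (SAP Section 12.9.8) reads "Ae(t1-t2) include Ae(0-2) (units), Ae(2-4) (units), Ae(4-6) (units), Ae(6-8) (units), Ae(8-10) and Ae(10-12) (units", which is six postdose intervals and no predose. Listing 41 (SAP Section 12.9.13) has the same six. The footnotes to Protocol Table 2 name the predose sample separately from the timed intervals.

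On collection, Protocol Section 5.1 states "Predose PK urine samples will be collected 0 to 2 hours before each time-matched dose on Days 1 through 5". Section 9.5.1 allows that, when the predose PK and bacteriology collections coincide, "a single urine sample of adequate volume may be collected and split into separate samples for PK and microbiological purposes". It refers collection procedures to the SRM and/or laboratory manual.

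**The concern.** Ae 12h, Ae(t1-t2), fe% and CLr on Days 1 and 4 are secondary endpoints. SAP Section 12.3.3 has the programmer derive all four, and Table 3 is where the rules are written. A programmer who follows Table 3 adds predose. One who follows the display notes does not. The two would report different Day 4 values from the same data.

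The difference runs one way. Prior gepotidacin is an exclusion (Protocol Section 6.2), so predose urine on Day 1 should contribute nothing. On Day 4 the predose sample follows six doses given about 12 hours apart. Adding it can only raise Day 4. CLr is the most exposed: Ae rises legitimately with accumulation, but under linear kinetics CLr should be the same on both days, so an inflated Day 4 numerator could read as a change in renal handling.

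**Working it through.** The plan gives no target or expected value for Ae 12h, fe% or CLr, and no Day 4 to Day 1 urine ratio, so there is no figure to reproduce. The check asks how much a literal sum would add.

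**Inputs from the documents.** Dosing about every 12 hours (Protocol Section 7.1), so the Day 4 time-matched dose is dose 7. Predose window of 0 to 2 hours (Protocol Section 5.1). About 285 mg of a single 1500 mg dose recovered unchanged in urine in a Phase I study, collection period not stated (Protocol Section 5.5).

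**Assumptions not in the documents.** Excretion rate proportional to a one-compartment oral profile; absorption rate ka = 1 per hour; half-life 3 to 12 hours; w hours of predose urine counted in full.

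**Formula.** Overstatement = Ae(−w to 0) / Ae(0 to 12) on Day 4. With k = ln 2 / half-life, at steady state and dropping the absorption term (negligible by 10 hours after a dose), this is close to

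[ka/(ka − k)] × [e^(−k(12−w)) − e^(−12k)] / [1 − e^(−12k)].

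- Half-life 3 h, w = 2: k = 0.2310; 1.300 × (0.0992 − 0.0625)/0.9375 = 0.051.
- Half-life 12 h, w = 2: k = 0.0578; 1.061 × (0.5612 − 0.5)/0.5 = 0.130. Integrating over the actual doses up to dose 7, when steady state is not quite complete, gives 0.129.

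Numerical integration with dose 7 as the Day 4 dose:

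| Half-life (h) | Overstatement, w = 1 h | Overstatement, w = 2 h | True Day 4/Day 1 ratio of Ae |
|---|---|---|---|
| 3 | 2.3% | 5.1% | 1.09 |
| 4 | 3.3% | 7.2% | 1.18 |
| 6 | 4.6% | 9.8% | 1.39 |
| 8 | 5.4% | 11.3% | 1.63 |
| 12 | 6.3% | 12.9% | 2.11 |

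On Day 1 the overstatement is 0%. Dropping the absorption phase (mono-exponential excretion) gives 5.9% to 12.2% for w = 2 at half-lives of 4 to 12 hours, so the range does not depend much on ka.

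**Effect on the derived parameters.** fe% scales with Ae 12h. Taking 285/1500 = 19.0% only as a reference level, 19.0 × 1.051 = 20.0% and 19.0 × 1.129 = 21.5%. CLr rises by the same 5% to 13% if it is divided by the 12-hour plasma AUC. If it were divided by the urine AUC that Table 3 defines, it would not be a renal clearance in the usual sense.

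**The gap before dosing.** Suppose predose is left out of the sum, the last void is up to 2 hours before the dose, and the 12-hour void is on time. Urine formed in the gap then falls into the 0 to 2 hour collection, and the same percentages apply with w equal to the gap. If the final void is early by the same gap, the net error is 0.0% to −0.1%.

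**The case against.** The strongest reply is that most of the text excludes predose. A predose interval cannot lie within 12 hours after the dose, the notes for Table 4.5 and Listing 41 list six intervals, and the protocol names predose separately. A careful programmer would probably leave it out. That stands: this is a contradiction to settle, and it does not show that Day 4 results will be biased.

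Several stronger readings are tempting, and the documents do not support them:

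- *Any drug from earlier doses in Day 4 urine is an error.* It is not. At steady state, Ae over a dosing interval properly includes it, as does the matching plasma AUC. Only counting more than 12 hours of urine is wrong.
- *The predose amount will certainly be computed and added.* It may not be computable. The sample may be one portion split with bacteriology, and the protocol states no total void volume for it. For the same reason, larger figures that assume a complete void holding several hours of urine have no basis in the documents.
- *The study collects up to 14 hours of urine because no void at dosing is required.* The protocol is silent on this and refers procedures to the SRM and/or laboratory manual, which may specify it. The 2-hour window is a maximum, and an equally early last void cancels the gap.

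The consequence is also limited. The urine endpoints are descriptive, no hypothesis is tested (SAP Section 2.4), Ro uses plasma AUC only, the steady-state model is for plasma only (SAP Section 7.1.4.1), and urine Cτ is unaffected.

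**Conclusion.** The point holds as a specification fault in a secondary endpoint. Table 3, coded literally, gives a Day 4 Ae 12h that covers more than 12 hours and disagrees with its own label and with the display notes. Day 1 gains no drug. If about two extra hours of urine were counted, Day 4 Ae 12h and fe% would be overstated by about 5% to 13%. CLr would be overstated equally, provided the plasma AUC is the denominator, which Table 3 does not say. The range rests on assumed half-lives of 3 to 12 hours, an absorption rate of 1 per hour, and a measurable predose amount. It is smaller than the true accumulation under the same assumptions (9% to 111%), but CLr has no such accumulation to mask it under linear kinetics. The possible gap between the predose void and the dose is a secondary point, open until the collection instructions are checked.

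**What to change.** In SAP Table 3, before programming:

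- Delete predose from the Ae(t1-t2) row.
- Define Ae 12h = Ae(0-2) + Ae(2-4) + Ae(4-6) + Ae(6-8) + Ae(8-10) + Ae(10-12).
- State that the predose sample is used for Cτ only.
- Name plasma AUC(0-τ) as the denominator of CLr.

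Secondary: confirm in the SRM or laboratory manual, or state in the protocol, that on Days 1 and 4 the bladder is emptied at time 0 and at 12 hours. If the manual already says so, a cross-reference is enough.

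The SAP change is a few words and needs no new data. The collection instruction needs no extra sample. Its small downside is a timed void on two days for participants who are already confined.
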